Pharmacodynamic response in these trials was assessed as glutaminase (GLS) activity in platelets and peripheral blood mononuclear cells (PBMCs) 4 hours after the first dose of CB-839 HCl on C1D1, or in solid tumor biopsy samples collected on C2D1 in early dose cohorts on study CX-839-001 (CB-839 Investigator's Brochure, 2017). A greater than 90% GLS inhibition was observed in platelets when Telaglenastat (CB-839) HCl levels exceeded 250 ng/mL. In solid tumor biopsies, a 75% inhibition of GLS activity was observed. Plasma glutamine concentrations were also monitored 4 hours post-dose on C1D1 and C1D15. All dose groups showed a 1.5- to 2-fold increase in plasma glutamine levels on C1D15, confirming GLS inhibition.

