## 5.8 Biomarker Plan

### List of Biomarker Assays in Order of Priority

Note for participating sites: Please see Section 5.1 for details on specimens to collect. The specimens tested are not always the same specimens that are submitted by the site, as processing of blood and tissue will occur at the Biobank prior to testing

Priority	Biomarker Name	Biomarker Assay	Biomarker Type and Purpose	M/ O	Timing	Specimen	Quantity Needed	Laboratory
1	EGFR mutational status	Any approved assay in tissue	Integral Eligibility criteria	M	Baseline	Archival tumor tissue	Per local guidelines	Local CLIA-certified labs (Standard of Care)
2	Quantification of plasma glutamine, glutamate, aspartate and asparagine concentrations	LC/MS/MS	Integrated To measure the pharmacodynamic effect of Telaglenastat (CB-839) HCl on systemic levels of TCA cycle metabolites.	M	Baseline, C1D15 (Dose escalation cohort only), C2D1, and at the time of disease progression.	Peripheral blood	3 mL blood in purple top EDTA tubes processed for plasma at site. 3 samples	[name] / Mayo Clinic Cancer Center (Mayo) Metabolomics Resource Core
3	WES	NGS	Integrated To confirm EGFR mutational status in tissue.	M	Baseline	DNA and cDNA from Archival tumor tissue	FFPE block or One (1) H&E slide, thirty to fifty (30-50) 5-10 micron unstained, air-dried, uncharged slides	[name] / MoCha, Frederick National Laboratory for Cancer Research (FNLCR)

Priority	Biomarker Name	Biomarker Assay	Biomarker Type and Purpose	M/ O	Timing	Specimen	Quantity Needed	Laboratory
4	PK for Telaglenastat (CB-839) HCl	LC/MS/MS	Integrated  To assess the PK of Telaglenastat (CB-839) HCl when administered in combination with Osimertinib (AZD9291).	M	All patients: Baseline  Dose escalation only: C1D15 following the AM dose of Telaglenastat (CB-839) HCl (pre-dose / 0 hr, 0.5 hr, 1 hr, 2 hr, 4 hr, 8 hr).  C2D1 following the AM dose of Telaglenastat (CB-839) HCl and Osimertinib (AZD9291) (0 hr, 0.5 hr, 1 hr, 2 hr, 4 hr, 8 hr, 24 hr a ).  Expansion cohort: C2D1 pre-dose.  All patients: A specimen will also be collected on Day 1 of each treatment cycle, starting with Cycle 3.	Peripheral blood	3 mL blood in purple top EDTA tube at each time point processed for plasma at the site.  At least 14 samples for a total of 42 mL of blood (including the C2D1 sample)	[name] / Mayo Clinic Cancer Center (Mayo) Pharmacology Shared Resource

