## 9.2 Sample Size/Accrual Rate

This study plans to accrue a minimum of 9 and a maximum of 28 patients. Estimated accrual rate is 5 patients/month.

NCI Protocol #: 10216  
Version Date: 09/17/2024  
Sample Size Justification:

For the dose escalation portion of the study, the trial will be conducted using a standard 3+3 dose escalation design. As there are three dose levels to be assessed, a total of 9 to 18 patients are expected to be enrolled depending on the number of dose escalations and assuming that a total of 6 patients will be treated at the final MTD/RP2D level.

In the expansion cohort component of the study, we plan to obtain additional data regarding safety and tolerability as well as preliminary efficacy of combination CB-839 and osimertinib. With a total of 16 patients at MTD/RP2D (6 + 10), we will estimate the ORR with a 95% confidence interval half-width of less than 25.4%, using the Clopper-Pearson exact method.

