All exploratory studies will be performed on specimens obtained from patients treated at MTD including the expansion cohort portion of the study. Graphical analyses will be largely used to assess potential patterns and relationships. cfDNA and circulating levels of glutamine, glutamate, aspartate, and asparagine will be summarized at baseline, after one month of treatment, and at time of progression. All continuous measurements will be summarized using mean +/- SEM, range, and median at each time point. Changes in these measurements from baseline to after treatment, or baseline to progression will be assessed using paired Wilcoxon tests. Adjustments for multiple comparisons or multiple outcomes will be performed using Bonferroni correction.  $^{18}\text{F}$ -FDG-PET parameters will also be summarized at baseline and after treatment using mean +/- SEM, range, and median. The changes in the FDG-PET/CT parameter measurements from baseline to after treatment will be compared between responders and non-responders using two sample t-test or Wilcoxon test, whichever is appropriate. Fisher's exact test will be used to assess the association between biomarkers, genetic alterations and response to study drugs. Logistics regression model might also be used to identify potential predictive and prognostic biomarkers beyond any genomic alteration with response to study drugs. Initially, data will be presented as summary statistics and upon sufficient accrual, a more detailed analytical plan will be developed. Given the small sample size, these analyses will be dependent on there being a sufficient number of responders with samples available.

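### Section 9.4 prescribes Bonferroni for the paired metabolite tests; Holm's step-down procedure controls the same error and never rejects less, so it is a free improvement (optional)

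*Combined protocol and SAP*

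**What the plan says.** Section 9.4 of the combined protocol and SAP covers these analyses in a few sentences.

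- Measurements: "cfDNA and circulating levels of glutamine, glutamate, aspartate, and asparagine will be summarized at baseline", after one month of treatment and at progression.
- Tests: "Changes in these measurements from baseline to after treatment, or baseline to progression will be assessed using paired Wilcoxon tests".
- Multiplicity: "Adjustments for multiple comparisons or multiple outcomes will be performed using Bonferroni correction".
- Analysis set: "All exploratory studies will be performed on specimens obtained from patients treated at MTD including the expansion cohort portion of the study". Section 9.2 plans 16 such patients, 6 from escalation and 10 from expansion.
- Sampling of the metabolites, from the biomarker table in section 5.8: "Baseline, C1D15 (Dose escalation cohort only), C2D1, and at the time of disease progression".

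Section 9.4 does not give the family of tests, the alpha, one- or two-sidedness, the exact or asymptotic form of the Wilcoxon test, or the expected number of pairs. The objective (1.3.4) is exploratory. Section 9.4 relies largely on graphical analyses and promises a more detailed analytical plan later.

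**The concern.** Bonferroni compares every p-value with the same small threshold, however many other hypotheses have already been rejected. Holm starts at that threshold and relaxes it after each rejection, with the same error guarantee. Choosing Bonferroni therefore gives up power and gains nothing.

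The loss could show here for two reasons. The samples are small, and an exact signed-rank test on few pairs has a smallest attainable p-value that may lie above the Bonferroni threshold. The two contrasts are also likely to have unequal numbers of pairs. A progression pair needs a patient who progresses on study and gives a sample. Section 6.4 lists several other ways for treatment to end, section 6.1 sets a date after which telaglenastat is unavailable, and section 6.5 follows patients for only 30 days after removal from study.

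What is at stake is which metabolite changes are declared significant. No dose or continuation decision rests on these tests.

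**Working it through.** **Stated figure.** The plan gives no power, family size or threshold for these tests, so there is none to reproduce. The figure that fixes n can be checked: Clopper-Pearson with 8/16 gives 24.65% to 75.35%, a half-width of 25.35%, which agrees with the limit of 25.4% in section 9.2.

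**Assumptions, none stated in the plan.** Family m = 4 metabolites × 2 contrasts = 8; familywise alpha 0.05; two-sided exact tests.

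**1. The floor under Bonferroni.** The threshold is 0.05/8 = 0.00625. The smallest two-sided exact p with n pairs is 2/2^n:

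- n = 7: 0.0156
- n = 8: 0.0078
- n = 9: 0.0039
- n = 16: 0.00003

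So 8 or fewer pairs can never reject, and 9 can.

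**2. How far the floor depends on the assumptions.**

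- A family of 4 per contrast gives 0.05/4 = 0.0125, which 8 pairs can meet. The same is true for any m up to 6 (0.05/6 = 0.0083).
- For m from 7 (0.0071) to 12 (0.0042), 9 pairs are needed. Adding cfDNA to one joint family would raise m above 8.
- One-sided, the minimum is 1/2^n. At n = 8 it is 0.0039, so 8 pairs can reject; at n = 7 it is 0.0078, so 7 cannot.
- With a normal approximation without continuity correction, the largest z is [n(n+1)/4]/√[n(n+1)(2n+1)/24]. At n = 9 this is 22.5/√71.25 = 2.67, p = 0.0077, so even 9 pairs would fail. At n = 10 it is 27.5/√96.25 = 2.80, p = 0.0051, which passes.

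**3. What Holm does to the floor.** Ordered p-values are compared with 0.05/8, 0.05/7, 0.05/6 and so on.

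- The first step is again 0.00625. If all eight tests have 8 or fewer pairs, Holm rejects nothing either.
- With exactly 8 pairs, a test becomes rejectable once two others have been rejected: 0.05/6 = 0.0083 > 0.0078.
- If all four progression tests have 7 or fewer pairs, the best case is four rejections at one month. That leaves 0.05/4 = 0.0125 < 0.0156, so Holm does not help.

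**4. Power.** Simulation with 20,000 runs per scenario, exact p-values, normal differences and independent tests. The shifts, in SD units, are assumed because the documents give no SD or planning effect. Entries are average power per real effect, in percent.

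| Pairs (one month / progression) | Real effects | Bonferroni | Holm | Gain |
|---|---|---|---|---|
| 10 / 10 | 2 of 8, 1.0 SD | 36.8 | 36.8 | 0.0 |
| 16 / 8 | 2 of 8, 1.0 SD | 36.3 | 36.5 | 0.2 |
| 16 / 12 | 2 of 8, 1.0 SD | 61.0 | 64.0 | 3.0 |
| 16 / 16 | 2 of 8, 1.0 SD | 73.0 | 75.2 | 2.2 |
| 16 / 16 | 4 of 8, 1.0 SD | 72.9 | 79.1 | 6.2 |
| 9 / 9 | 8 of 8, 0.8 SD | 11.7 | 13.4 | 1.7 |
| 12 / 12 | 8 of 8, 0.8 SD | 28.2 | 37.3 | 9.1 |
| 16 / 16 | 8 of 8, 0.8 SD | 47.8 | 63.5 | 15.7 |
| 16 / 16 | 8 of 8, 1.2 SD | 89.9 | 98.9 | 9.0 |
| 16 / 10 | 8 of 8, 1.2 SD | 72.1 | 89.4 | 17.3 |
| 16 / 8 | 8 of 8, 1.2 SD | 44.9 | 76.2 | 31.3 |
| 16 / 8 | 8 of 8, 2.0 SD | 50.0 | 99.6 | 49.6 |
| 16 / 7 | 8 of 8, 2.0 SD | 50.0 | 50.0 | 0.0 |

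The chance of at least one true rejection agreed within 0.2 points in every scenario. Familywise error was at most 4.3% for both methods.

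With unequal shifts (1.5, -1.2, -0.8 and -0.8 SD at both times, correlation 0.4) and 16 / 8 pairs, the four progression tests have 0% power under Bonferroni and 61%, 44%, 23% and 23% under Holm. With 16 / 10 pairs, the two weaker metabolites go from 48-49% to 66-67% at one month and from 20-21% to 39% at progression. Halving all these shifts cuts the gains to about 0.4 to 3 points.

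**The case against.** Bonferroni is valid, prespecified and conservative, and the analysis is exploratory and mainly graphical. All of that stands, so the point is optional. Three stronger readings are tempting, and the documents support none of them.

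- A reader might infer that Holm cures the small-sample floor. It does not: its first threshold is the same, and within the range of 8 or fewer pairs it helps a contrast only at exactly 8.
- A reader might infer that the progression contrast will have 8 or fewer pairs. That is possible, but the plan gives no expected number, and section 5.8 makes the progression sample mandatory. With 16 planned patients, the one-month contrast reaches the floor only if half or more lack a pair.
- A reader might infer that glutamine is sure to reject first and open the way for the rest, because section 2.2.1.3.1 reports "All dose groups showed a 1.5- to 2-fold increase in plasma glutamine levels on C1D15". Those levels were taken 4 hours after a dose in monotherapy studies. In this trial the C2D1 metabolite sample is taken before the dose, on the combination (sections 5.1.1 and 5.1.2), and the half-life is about 4 hours. The earlier rise cannot simply be carried over.

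It is also fair to say that the undefined family matters as much as the choice of method. With four tests per contrast, Bonferroni itself can reject with 8 pairs.

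**Conclusion.** The point holds as an efficiency gain and not as a validity error. That Holm controls the same familywise error and never rejects fewer hypotheses needs no assumption beyond those of Bonferroni.

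The size of the gain is conditional. It is about 0 to 3 points of power per real effect when two of eight changes are real, and roughly 10 to 30 points when most are real and there are 12 to 16 pairs at one month. It can be larger at exactly 8 progression pairs with very large shifts, and it is small when pairs are few throughout. The floor at 8 pairs rests on eight exact two-sided tests at familywise 0.05, and all the power figures rest on assumed shifts.

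**What to change.** In section 9.4, replace Bonferroni correction with the Holm step-down procedure. In the same sentence, or in the detailed analytical plan that section 9.4 promises, state:

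- the family (for example four metabolites by two contrasts, and whether cfDNA belongs to it);
- the familywise alpha and the sidedness;
- that the exact signed-rank test is used;
- the smallest number of pairs at which a contrast will be tested rather than only described.

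Settle this before the metabolite data are examined. The cost is a sentence or two of text. It needs no new samples or patients and loses no error control.

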In the expansion cohort, patients will receive combination Telaglenastat (CB-839) HCl at 800 mg orally twice daily and Osimertinib (AZD9291) 80 mg orally daily. This is based on results of the dose escalation cohort where combination Telaglenastat (CB-839) HCl and Osimertinib (AZD9291) at these doses were associated with acceptable safety and toxicity profile. In total, 12 patients were treated with combination Telaglenastat (CB-839) HCl and Osimertinib (AZD9291) in the dose escalation study, with one patient experiencing DLT at dose level 3 (grade 3 mucositis and grade 2 pneumonitis, which is protocol defined DLT). Both mucositis and pneumonitis are known toxicities with osimertinib, and both resolved with supportive care and withholding of study therapy. Treatment related serious adverse events (TRSAE) occurred in 2 patients, including grade 3 lymphocyte count decreased (attributed to osimertinib) in one patient as well as grade 3 fatigue (attributed as possibly related to both study agents and likely related to disease), and grade 3 failure to thrive (attributed as possibly related to CB-839 and definitely related to disease). The most common treatment related adverse events of any grade were nausea (n=6, 50%, all grade 1 or 2), fatigue (n=4, 33%), and decreased white blood cell count (n=4, 33%). Best response was complete response (CR) in 1 patient, stable disease (SD) in 7 patients, and disease progression in 4 patients. Of note, all 6 patients treated at the highest dose level tested had stable disease as best response after experiencing progression on osimertinib. As 800 mg BID is the highest dose that is confirmed to be safe and well tolerated in single-agent and combination Telaglenastat (CB-839) HCl studies, and there were no new safety concerns as well as evidence of clinical activity seen in the dose escalation cohort, Telaglenastat (CB-839) HCl at 800 mg orally twice daily and Osimertinib (AZD9291) 80 mg orally daily was chosen for the expansion cohort.

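### Genetic and biomarker associations rest on tumour response in at most 16 RP2D patients, six already known to be non-responders, with no fallback outcome named although tumour size is measured every 8 weeks

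*Combined protocol and SAP*

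**What the plan says.** Section 9.4 states that "Fisher's exact test will be used to assess the association between biomarkers, genetic alterations and response to study drugs". It adds that a logistic model might be used to look for predictive and prognostic biomarkers. The analysis set is restricted: "All exploratory studies will be performed on specimens obtained from patients treated at MTD including the expansion cohort portion of the study". The same section closes with a caveat that "these analyses will be dependent on there being a sufficient number of responders with samples available".

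Section 9.2 counts 16 patients at the MTD/RP2D, 6 from escalation and 10 from expansion. Section 2.3 (rationale for the expansion dose) fixes the dose: "In the expansion cohort, patients will receive combination Telaglenastat (CB-839) HCl at 800 mg orally twice daily and Osimertinib (AZD9291) 80 mg orally daily". That is the top escalation level, and there "all 6 patients treated at the highest dose level tested had stable disease as best response". For the whole escalation cohort of 12, "Best response was complete response (CR) in 1 patient, stable disease (SD) in 7 patients, and disease progression in 4 patients". The single complete response therefore came from a lower dose level and lies outside the exploratory set.

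Section 12.1.2 requires a sum of target-lesion diameters at baseline, and the Study Calendar (11.1) repeats tumour measurements every 8 weeks until progression. Section 12.1.4.1 turns that sum into a partial response at a decrease of 30% or more. Section 9.4 does not use the sum as an outcome.

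**The concern.** Response, most naturally read here as responder versus non-responder, is the only outcome against which section 9.4 names a test for genetic alterations. Six of the 16 patients are already fixed as non-responders, so the number of responders may be too small for the named test to separate any marker groups. Calling all six "stable" also discards whatever differences in tumour shrinkage exist among them.

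What is at stake is the part of objective 1.3.6 that seeks predictive markers from sequencing of archival tissue, a specimen listed as mandatory in the Biomarker Plan (5.8). The scans taken for response assessment already carry a graded measure that would use all the patients.

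**Working it through.** **1. The plan's own figure.** For the 16 patients section 9.2 says "we will estimate the ORR with a 95% confidence interval half-width of less than 25.4" percent. The Clopper-Pearson interval is widest at 8 of 16: limits 0.2465 and 0.7535, half-width (0.7535 − 0.2465)/2 = 0.2535. The figure reproduces. It concerns the ORR only; no power or effect size is given for the biomarker tests.

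**2. How many responders to expect.** All responders come from 10 patients, so R ~ Binomial(10, p). The current text sets no target ORR, so p = 10% to 30% is assumed. The nearest figure in the documents is 24.6% for osimertinib alone in T790M-negative disease (2.2.2.3.3), which is a different population. P(R ≤ 1) = (1−p)^10 + 10p(1−p)^9:

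- p = 0.10: 0.349 + 0.387 = 0.736
- p = 0.20: 0.107 + 0.268 = 0.376
- p = 0.30: 0.028 + 0.121 = 0.149

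**3. Smallest attainable two-sided Fisher p-value, n = 16.** An alpha of 0.05 is assumed, since none is stated.

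- One responder, most favourable table: 1/16 = 0.0625. No marker can reach 0.05.
- Split 8/8, all r responders on one side: p = 2·C(8,r)/C(16,r). For r = 2, 3, 4, 5 this is 56/120 = 0.467, 112/560 = 0.20, 140/1820 = 0.077 and 112/4368 = 0.026. Five responders are needed. P(R ≥ 5) = 0.2%, 3.3% and 15% at p = 10%, 20% and 30%.
- Split 4/12, all responders marker-positive: r = 2 gives 6/120 = 0.05 exactly; r = 3 gives 4/560 = 0.007. Rarer markers need fewer responders.

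**4. Exact Fisher power**, by enumeration with the six escalation patients fixed as non-responders, two-sided 0.05:

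| Response, marker-positive vs negative | 50% positive | 30% positive |
|---|---|---|
| 30% vs 10% | 2% | 5% |
| 40% vs 10% | 6% | 10% |
| 50% vs 10% | 14% | 18% |
| 60% vs 0% | 40% | 44% |

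A zero cell, at which a logistic model separates or cannot be estimated, occurs with probability 62% to 100% across these eight cases.

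**5. Fisher on response versus Wilcoxon on best percentage change.** Simulation with normal percentage change, a responder being a decrease of 30% or more, and the six escalation patients held between −30% and +20%. Scenario A: 25-point difference, SD 20. With group means 0 and −25 the ORR is [Φ(−1.5) + Φ(−0.25)]/2 = (0.067 + 0.401)/2 = 23%. Scenario B: 20-point difference, SD 15, ORR (0.023 + 0.252)/2 = 14%. The 4/12 rows keep those overall ORRs.

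| Marker split | Scenario | Fisher | Wilcoxon |
|---|---|---|---|
| 8/8 | A | about 1% | about 50% |
| 8/8 | B | about 0.1% | about 60% |
| 4/12 | A | about 20% | about 34% |
| 4/12 | B | about 18% | about 42% |

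The values move by a few points with the way the six patients are conditioned. The 4/12 Fisher figures count p = 0.05 exactly as significant; a strict p < 0.05 would need three responders and lowers them.

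**6. Sensitivity.** SD 25, ORR 10% to 30%, differences of 1, 1.5 and 2 SD:

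- 50% marker-positive: Fisher 0.2–7%, 0.2–14%, 0–17%; Wilcoxon 28–30%, 55–59%, 79–83%.
- 25% marker-positive: Fisher 4–14%, 6–26%, 7–43%; Wilcoxon 21–22%, 39–43%, 55–66%.
- Bonferroni over an assumed four markers (0.05/4 = 0.0125), both prevalences: Fisher 0–21%, Wilcoxon 7–60%.
- Bonferroni over an assumed ten markers, scenarios A and B: Wilcoxon about 16–22% at 8/8 and 8–11% at 4/12.

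**The case against.** The plan is candid about this limit. Section 9.4 says the work will be largely graphical, that summary statistics come first, that a fuller plan will follow on sufficient accrual, and that responders may be too few. The Biomarker Plan labels the sequencing exploratory and hypothesis-generating. No decision rests on these tests; the primary endpoints are safety, tolerability and RP2D. All of this stands, and it makes the point a modest one. But the caveat names the condition most likely to fail and says nothing about what happens then.

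A reader might infer that Fisher's test has almost no power whatever the marker. That goes too far. It reaches 40–44% for 60% versus 0% response, and the gap to Wilcoxon narrows for markers carried by about a quarter of patients.

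A reader might also infer that objective 1.3.6 becomes unanswerable. The documents do not support that. Its resistance-mechanism part need not be a response association. Serial cfDNA up to progression also bears on resistance, and section 9.4 relates PK and PD markers to clinical outcomes by mixed models or GEE.

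Finally, the Fisher sentence does not say that response is binary. That is inferred from the logistic model and from the responder versus non-responder comparison for PET in the same section. Section 9.5.2 lists several response categories, and Fisher's test can handle more than two. Binary remains the likelier reading.

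**Conclusion.** The point holds in a limited form. At most 16 patients enter these analyses, six cannot be responders, and one responder or none is a realistic result (15% to 74% over the assumed ORR range). In that case no Fisher test can reach 0.05. For common markers the test stays weak even with several responders. Best percentage change did better in every scenario with a real effect, but it does not rescue a sequencing-wide search: at a 1 SD difference its power is only about 21–30%, and lower after Bonferroni.

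The facts on the analysis set, the six stable-disease patients and the recorded tumour sums come from the documents. The ORR range, marker prevalence, effect sizes, SDs, alpha and number of markers are assumptions. Missing specimens or exclusions after central EGFR testing would reduce the set below 16.

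**What to change.** In section 9.4, or in the fuller analytical plan it promises, add best percentage change from baseline in the sum of target-lesion diameters as an exploratory outcome for biomarker associations:

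- Wilcoxon rank-sum for binary markers and Spearman correlation for continuous ones.
- Count only measurements up to progression.
- Rank as worst the patients with no post-baseline scan, and those whose first post-baseline assessment is progression by new or non-target lesions. Without the second rule such a patient could rank well on target lesions alone.
- Keep Fisher's test on response as a descriptive table.
- Label the outcome as added after the escalation responses were known. Section 13.1 gives the protocol PI and statistician data access at all times, and the summary of changes records that accrual is closed, so it cannot be presented as fully prespecified.

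No new visit, scan or specimen is needed. The cost is the wording, a ranking rule and the post hoc label.
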